1 BACKGROUND AND PROTOCOL HISTORY

Mixed urinary incontinence (MUI), defined as the presence of both stress urinary incontinence and urgency urinary incontinence, is a challenging condition for which clinicians frequently use multiple sequential treatments that have undergone limited head to head comparison in rigorous clinical trials.

Mid-urethral Sling vs. Botox A (MUSA) is a randomized 2-arm clinical trial for women who have at least moderate bother from both stress and urgency incontinence and who have failed one or more conservative treatments. The primary objective is to estimate the effect of 100 units of intradetrusor injections of Botulinum toxin A (Botox A ®) compared to mid-urethral sling surgery for the treatment of MUI. Participants in the Botox A arm may receive one additional injection of 100 units Botox A between 3 months and 6 months after the initial injection if they have persistent urgency incontinence symptoms and meet the safety criteria. MUSA will randomize 146 women to treatment with Botox or Sling in a 1:1 ratio.

MUSA was originally designed as a 6-month trial and began enrolling participants in June 2020. Protocol amendment 4.0 approved by the DSMB in February 2021 added an observational 6-month follow-up period, with phone assessments at 9 and 12 months. At the time of transitioning to protocol version 4.0, 2 participants had already completed the study at 6 months and did not give consent to participate in the follow-up period.

At the completion of this study, we will better understand whether a surgical treatment that focuses on the urgency component (Botox A) is superior to a surgical treatment that focuses on the stress component (mid-urethral sling). The trial will provide clinically useful information for two treatments that are widely used to treat MUI but for which evidence-based data are not available.

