Patient Global Impression of Severity at 3, 6, 9, 12 months	Dichotomous 1 = Normal/Mild 0 = Moderate/Severe	The Patient Global Impression of Severity score will be computed at baseline and 6 months (and 3, 9, and 12 months). For defining binary severity of urinary tract condition, a scale response of "Normal" or "Mild" will be set to "Normal/Mild". Scale responses of "Moderate" or "Severe" will be set to "Moderate/Severe". If data at an assessment time point are missing, the outcome variable will be coded as missing.
Patient Global Symptom Control at 3, 6, 9, 12 months	Dichotomous 1=adequate leakage control 0 = inadequate leakage control	The Patient Global Symptom Control score will be computed at 6 months (and 3, 9, and 12 months). The statement "My current treatment is giving me adequate control of my urine leakage" is scored on a scale from 1 (strongly disagree) to 5 (strongly agree). If the response is scored 1, 2, or 3, coded as "inadequate leakage control". If the response is scored 4 or 5, coded as "adequate leakage control".
		A score \leq 3 is required to meet the criteria for additional Botox injection.
Had protocol-specified additional Botox between 3- 6 months	Dichotomous 1=yes 0=no	 = yes for women who received Botox as the main study treatment and also received the additional 2nd allowed Botox treatment prior to 6 months, = no otherwise
		For participants who received MUS as their main study treatment, this indicator will be coded to missing.
Additional treatment up to 6 months, and	Dichotomous 1=yes 0=no	The types of additional treatment for SUI and/or OAB will be identified and categorized from the Additional Therapy form.

Variable	Туре	Definition
Additional treatment between 6 and 12 months		An indicator of additional treatment will be calculated for each subject where subjects with additional treatments identified below will be assigned "Yes", otherwise subjects are assigned "No". The rate of receiving additional treatment is calculated as the percentage of participants with indicator ="Yes" among all non-missing indicators.
		This includes anyone who had a crossover treatment (MUS to Botox, or Botox to MUS), in addition to any other type of UI/OAB treatment or medication.
		If a participant is missing the visit required to derive additional treatment timing (6 month or 12 month), the visit window close date (6 or 12 months from treatment + 30 days) was used in place of the missing visit date.

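### The additional-treatment indicator is never set to missing, so women not followed in an interval count as untreated and the reported rate is a lower bound

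*SAP*

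**What the plan says.** SAP section 9.2 defines two indicators of additional treatment for SUI or OAB: up to the 6-month visit, and from that visit to 12 months. Cross-over to the other study treatment counts. Treatments are "identified and categorized from the Additional Therapy form", which the flow chart in SAP section 4.6 lists in the as-necessary column rather than at a scheduled visit.

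A woman with a listed treatment is Yes and every other woman is No. The summary is then defined: "The rate of receiving additional treatment is calculated as the percentage of participants with indicator" equal to Yes, "among all non-missing indicators". Nothing in the entry says when the indicator is missing. If the 6- or 12-month visit did not take place, "the visit window close date (6 or 12 months from treatment + 30 days) was used in place of the missing visit date", and the indicator is still derived.

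SAP section 3.2.3 lists additional treatment, within 6 months and during the follow-up to 12 months, as an exploratory efficacy outcome. Section 9.4 compares the arms by chi-squared or Fisher's exact test. The protocol addendum allows other treatments, including that of the other arm, after 6 months. SAP section 1 records that "2 participants had already completed the study at 6 months and did not give consent to participate in the follow-up period".

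**The concern.** If a woman was not contacted, the absence of a form does not show that she had no treatment; it shows that nobody could record one. The text refers to non-missing indicators but supplies no rule that would create a missing one. A programmer following it literally puts unobserved women in the denominator as untreated.

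The error can only lower the rate. It is largest in months 6 to 12, when extra treatment is permitted and cumulative loss is greatest. At stake is the accuracy of a descriptive result: how many women in each arm went on to another treatment. The primary UDI analysis does not use this indicator.

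**Working it through.** **Is there a rule elsewhere that removes these women?**

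- The date substitution in section 9.2 helps place a recorded treatment in one interval or the other. It does not give an unobserved woman a missing status.
- The mITT population (SAP section 5.1) requires study treatment and some post-baseline efficacy data. It removes women lost before any assessment, but not those who were seen at 3 or 6 months and then left.
- For PGI-I, a scheduled assessment in the same table, the rule is explicit: "If data at an assessment time point are missing, the outcome variable will be coded as missing". No equivalent appears for additional treatment.

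**The plan's own figures.** The documents state no rate of additional treatment, so there is none to reproduce. The one stated figure that uses 12-month attrition is 88% power for the 12-month UDI total (SAP section 6). Its inputs are a difference of 26, SD 46.5, two-sided alpha 0.05, 5% loss by 6 months and a further 5% by 12 months. With 73 × 0.90 = 65.7 women per arm, a noncentral-t calculation gives 88.6% (65 per arm) to 89.0% (66 per arm), in line with 88%. This confirms about 10% as the planned cumulative loss; it says nothing about the indicator itself.

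**Effect of the coding.** Let r be the rate among followed women and u the share wholly unobserved in the interval.

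- Reported rate = r × (1 − u)
- Shortfall if unobserved women were treated at the same rate = r × u

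The values of u come from the documents: 2/146 = 1.4% for the non-consenters, 5% and about 10% as planned (SAP section 6), and 9% and 12% as the 12-month discontinuation in ROSETTA and ESTEEM (protocol addendum). The values of r are assumptions. Reported rates are:

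| u | r = 10% | r = 20% | r = 30% | r = 40% |
|---|---|---|---|---|
| 1.4% | 9.9% | 19.7% | 29.6% | 39.5% |
| 5% | 9.5% | 19.0% | 28.5% | 38.0% |
| 9% | 9.1% | 18.2% | 27.3% | 36.4% |
| 10% | 9.0% | 18.0% | 27.0% | 36.0% |
| 12% | 8.8% | 17.6% | 26.4% | 35.2% |

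The two non-consenters alone cost 0.1 to 0.5 points. At u = 10% the shortfall is 1 to 4 points.

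**How much of the 10% is really unobserved?** It is the sum of 5% lost before 6 months and 5% lost between 6 and 12 months. The second group is observed up to the point of leaving, and the addendum includes a 9-month call. With r = 30%, the shortfall is 0.30 × 0.05 = 1.5 points if only the first group is unobserved, and 0.30 × 0.10 = 3.0 points if both are wholly unobserved.

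**If lost women differ.** Suppose unobserved women were treated at twice the followed rate (an assumption). At r = 30% and u = 10% the true rate is 0.27 + 0.60 × 0.10 = 33%, a shortfall of 6 points. The extreme bounds on the true rate are 27% (none of them treated) and 0.27 + 0.10 = 37% (all treated).

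**The case against.** The strongest reply is that the gap is one of wording. By naming non-missing indicators the SAP implies that a missing category was intended, and the date substitution can be read as a device for timing only. That is fair as to intent. But the operative sentence assigns No to everyone else, so anyone following the text produces the lower rate.

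A second reply is that this coding is not peculiar to one variable, and that stands. Sling revision, UTI, urinary retention, residual urine volume, catheterization, pelvic pain and dyspareunia, all taken from forms or logs, have the same No default in section 9.2. A reader might infer from the PGI-I rule that additional treatment is treated as an exception; the table does not support that. The SAP has one convention for scheduled assessments and another for reported events. The event convention is weakest where follow-up ends early and events are expected late, as here.

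A third reply is that 10% overstates the unobserved share. This also stands. Some early losses are removed by the mITT definition, later losses are partly observed, a treatment recorded before a woman left still counts as Yes, and SAP section 7.10 says coordinators pursued visits outside the window. The planned CONSORT diagram (SAP section 8.1) will also show how many women discontinued in each period.

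**Conclusion.** The point holds at a modest size. As written, the rate is a lower bound. The shortfall is 0.1 to 0.5 points from the two documented non-consenters. It reaches about 3 points on an assumed 30% if the full planned 10% were unobserved. It exceeds that appreciably only if lost women sought treatment more often than followed women. The addendum ties retention to the freedom to pursue other treatment, so loss unrelated to treatment-seeking should not be taken for granted; nor do the documents show the opposite. Actual loss and treatment rates are not given.

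Two stronger readings are not supported:

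- **That the comparison between arms is biased.** This needs different loss by arm. Assumed losses of 5% and 15% would turn equal rates of 30% into 0.30 × 0.95 = 28.5% and 0.30 × 0.85 = 25.5%. No document suggests such a split. The 3-point artefact is also small beside the standard error of the difference, √(2 × 0.30 × 0.70 / 73) = 7.6 points.
- **That cross-over by 12 months is a main result.** The addendum's 12-month primary outcome is change in UDI total and its secondary outcomes are UDI subscales. Additional treatment is exploratory, and SAP section 7.8 makes its p-values descriptive.

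**What to change.** Preferred: report the cumulative incidence of first additional treatment by arm (Kaplan-Meier), from study treatment and censored at last contact, read at 6 and 12 months. If a separate figure for months 6 to 12 is wanted, start the clock at the 6-month visit. This uses the partial follow-up from the 9-month call. It assumes that censoring is unrelated to treatment-seeking, so keep the all-No coding as a lower-bound sensitivity analysis.

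Minimum: add one sentence to section 9.2 setting the interval indicator to missing for a woman with no follow-up contact in that interval and no recorded treatment. Partly followed women then stay No, so a smaller understatement remains. Do not drop partly followed women coded No while keeping partly followed women coded Yes; that would bias the rate upward.

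In either case, report the number followed per arm and interval beside the rate. The cost is one SAP sentence and a small derivation change, with a slightly smaller denominator or one extra survival-type analysis. No new data are needed.

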To address the issue of surgeon certification for Botox intradetrusor injection and to ensure standardized training of all surgeons, all “certified surgeons” administering injections will be required to view a short instructional video demonstrating optimal techniques and detailing sites of drug injection in a standardized manner. In addition, “certified surgeons” at each site must have previously performed a total of 10 intradetrusor injection procedures.

5.2.2 *Standardization of Botox Injection Procedures*

Detailed standardization of the surgical procedure will be developed and will include the following key points:

1. The Coordinator will ensure that the subject has been instructed regarding the proper technique for clean intermittent self-catheterization (CISC) and will confirm that the subject or designated caretaker is able to perform the task.

2. Within one week prior to injection, a confirming urine pregnancy test will be performed in all premenopausal women. A urine dip to rule out infection will also be performed. If the urine dip is positive the participant will be treated for a urinary tract infection and rescheduled within 4 weeks for Botox A® injection visit.
3. The bladder will be catheterized and 50 ml of 2% lidocaine placed in the bladder and 10 ml of 2% lidocaine jelly in the urethra. The subject will be asked to lie on their left and right lateral decubitus for several minutes at a time to ensure diffuse anesthetic effect on the bladder. Cystoscopic surveillance of the bladder will be used to confirm normality.

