5.3 Safety (SAF) Population

The safety population will comprise all subjects who were randomized and treated, grouped by the treatment to which they actually received (for any situations in which a participant was not initially treated with their randomized treatment assignment). If all patients received their randomized treatment and have some post-baseline efficacy data, then the safety population would be the same as the mITT.

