		Indicators will be created for overall additional treatment and the following individual categories:
		Up to 6 months (up to the day before the 6 months visit):
		MUS for Botulinum toxin A arm
		Botulinum toxin A for MUS arm
		OAB/UUI medication
		Behavioral Therapy
		Physical Therapy / Biofeedback
		PTNS
		Continence pessary / POISE Impressa
		Sacral neuromodulation
		Bulking injections
		6-12 months (starting the day of the 6 months visit)
		Mid-urethral Sling placement

Variable	Туре	Definition
		Botulinum toxin A injection
		OAB/UUI medication
		Behavioral Therapy
		Physical Therapy / Biofeedback
		PTNS
		Continence pessary / POISE Impressa
		Sacral neuromodulation
		Bulking injections
Safety outcomes		Adverse events are reported for a participant from the date they are randomized to the date that they exit the study. There were 9 adverse events that were collected after randomization but occurred before treatment. The majority of these were UTIs (n=8), with one "Fall" event that is important documentation leading into a subsequent serious adverse event.
Sling Revision or removal at	Dichotomous	An indicator of sling revision/removal will be calculated for each subject where those
any time	1=yes 0=no	who have a sling revision/removal listed on the Additional Therapy form will be assigned a "Yes", otherwise subjects are assigned "No".
		At final database lock reviews, one "sling removal" was identified from the Additional Therapy form. Adverse events were further reviewed for implemented actions of "explant" or "surgical intervention" but yielded no further cases identified. An adverse event form was requested to be entered for the single reported removal.
		The rate of sling revision is calculated as the percentage of participants with indicator equal to "Yes" among all non-missing indicators.

Variable	Туре	Definition
Sling mesh exposure	Dichotomous 1=yes 0=no	An indicator of sling mesh exposure will be calculated for each subject (yes/no) using the MEDRA coded preferred term of reported adverse events. Subjects will be coded to "Yes" if they have any adverse event with a MEDRA preferred term of "Medical device site erosion", or if the verbatim adverse event term includes text strings "Mesh", "Mesh exposure", or "MUS mesh exposure". Two cases were identified from adverse event forms at final database lock review.

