Rate of Urinary Tract Infection (UTI) Events	Dichotomous 1=yes 0=no	The frequency of acute UTI events will be taken from all adverse event reporting forms submitted for a participant. The outcome variable will be coded with a value of "Yes" if the participant had any reported acute UTIs over their study duration, identified by MEDRA coding preferred term of "Urinary tract infection" and "recurrent" is NOT specified by verbatim adverse event term or comments. If no acute UTI events were reported for a participant, the outcome variable will be coded with a value of "No".Final database lock review took efforts to query sites for participants with questionable urine test results and get PI confirmation that all necessary events had been reported.
Rate of recurrent Urinary Tract Infection (UTI) Events	Dichotomous 1=yes 0=no	The frequency of recurrent UTI events will be taken from all adverse event reporting forms submitted for a participant. The outcome variable will be coded with a value of "Yes" if the participant had any reported recurrent UTIs over their study duration, identified by MEDRA coding preferred term of "Urinary tract infection" and "recurrent" is specified by verbatim adverse event term or comments. If no recurrent UTI events were reported for a participant, the outcome variable will be coded with a value of "No". Final database lock review took efforts to query sites for participants with questionable urine test results and get PI confirmation that all necessary events had been reported.
Rate of Urinary Retention Events	Dichotomous 1=yes 0=no	The frequency of urinary retention events will be taken from all adverse event reporting forms submitted for a participant. The outcome variable will be coded with a value of "Yes" if the participant had any reported urinary retention over their study duration,

Variable	Туре	Definition
		identified by MEDRA coding preferred term of "Urinary retention". If no urinary retention events were reported for a participant, the outcome variable will be coded with a value of "No".
		Final database lock review took efforts to query sites for participants with reported self- catheterization logs or questionable post void residual results (>200mL, aside from visits immediately post-surgery) and get PI confirmation that all necessary events had been reported.

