10.2 Adverse Events/Complications/Adverse Symptoms

MUSA complications are divided into "adverse symptoms" and "adverse events".

Participants were asked to report any adverse events or adverse symptoms from randomization through 12 months follow-up. All adverse events were collected on an adverse event log and coded using MedDRA (V24.0). In addition, a few adverse symptoms are captured as part of the PRO questionnaires.

Adverse symptoms will be captured using an active approach using validated questionnaires and an open-ended approach.

- a. Active capture for specific patient-reported adverse symptoms will be identified by responses on validated questionnaires These 3 adverse symptoms are patient report of new or worsening: 1) pelvic/vaginal pain, 2) sensation of incomplete bladder emptying (based on UDI responses) and 3) dyspareunia (based on PISQ-IR response). These are captured at 3, 6, 9, and 12 months.
- b. Open-ended capture for adverse symptoms will also be captured using the open-ended approach and recorded on the AE log. Symptoms of interest include: 1) New/worsening partner dyspareunia and 2) New/worsening constipation. Using the open-ended approach, symptoms are captured if reported by the participant and documented on the Adverse Event log.

Adverse events will be captured using the standard AE open-ended capture approach using chart review, physician report, or patient report corroborated by medical documentation and recorded on the Adverse Event log.

A table summarizing the Adverse Events and Adverse symptoms of interest is as follows (all variable definitions are included in Section 9.2):

Postoperative complications	
Adverse symptom	Definition
*New/worsening abdominal/genital pain at or beyond 3 month visit	UDI item N captured at 3, 6, 9, and 12 months and per patient report, chart review, physician report
*New/worsening dyspareunia at or beyond 3 month visit	PISQ item C5 captured at 3, 6, 9, and 12 months and per patient report, chart review, physician report
*New/worsening report of difficulty emptying bladder at or beyond 3 months	UDI item J captured at 3, 6, 9, and 12 months and per patient report, chart review, physician report
New/worsening partner dyspareunia at or beyond 3 month visit	Per patient report, chart review, physician report

Adverse Event	
Postop need for catheter and/or ISC at or beyond 2 weeks (sling or Botox)	Captured by chart review, physician report, exam, or patient report corroborated by medical documentation

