Vaginal mesh exposure (sling only)	Captured by chart review, physician report, exam, or patient report corroborated by medical documentation
Vaginal mesh erosion into organ (sling only)	Captured by chart review, physician report, exam or patient report corroborated by medical documentation
Other wound healing problems >6 weeks (sling only)	Captured by chart review, physician report, exam or patient report corroborated by medical documentation
New/worsening vaginal infection (sling or Botox)	Captured by chart review, physician report, exam, or patient report corroborated by medical documentation
Urinary tract infection beyond 2 weeks (sling or Botox)	UTI based on clinical judgment or confirmation of culture proven, also includes empiric antibiotic treatment for symptoms thought to be due to UTI, or patient report corroborated by medical documentation. If a culture is sent that turns out to be negative, this would not be classified as a UTI. Captured by chart review, physician report, or patient report corroborated by medical documentation
Other infection possibly related to intervention (sling or Botox)	Infection diagnosed using clinical or radiologic indicators – not including vaginal infection, UTI Captured by chart review, physician report, or patient report corroborated by medical documentation
Non-study health care provider visit due to complication related to intervention (sling or Botox)	Captured by chart review, physician report, or patient report corroborated by medical documentation
Emergency room visit due to complication related to intervention (sling or Botox)	Captured by chart review, physician report, or patient report corroborated by medical documentation
Hospital readmission related to intervention (sling or Botox)	Captured by chart review, physician report, or patient report corroborated by medical documentation
Reoperation related to surgery (any return to OR for issue related to intervention (e.g. recurrent SUI, UUI/OAB) (sling only)	Captured by chart review, physician report, or patient report corroborated by medical documentation
An adverse event that is "unexpected" and "possibly, probably or definitely related"	Captured by chart review, physician report, or patient report corroborated by medical documentation

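### SAP 9.2 and 10.2 state different windows for UTI, and the 9.2 rule as written takes in 8 infections that preceded treatment

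*SAP*

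**What the plan says.** **SAP 9.2 (safety outcomes).** Adverse event reporting runs from randomization to study exit. The section discloses: "There were 9 adverse events that were collected after randomization but occurred before treatment. The majority of these were UTIs (n=8". The ninth event is a fall. No rule says whether these events enter the safety variables.

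The UTI variable draws on all adverse event forms and is Yes if "the participant had any reported acute UTIs over their study duration", provided that the word recurrent "is NOT specified by verbatim adverse event term or comments". The recurrent-UTI variable is Yes if "the participant had any reported recurrent UTIs over their study duration". Neither refers to the treatment date.

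**SAP 10.2.** A table headed as postoperative complications has the row "Urinary tract infection beyond 2 weeks (sling or Botox". Its definition cell covers how a UTI is diagnosed and from what source, not when. The text introducing the table says that "all variable definitions are included in Section 9.2".

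**SAP 5.3.** "The safety population will comprise all subjects who were randomized and treated", grouped by treatment actually received.

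**Aim.** Comparing the proportions of women with UTI and recurrent UTI between groups is part of the safety aim (Protocol 1.2, SAP 3.1.2) and a listed safety outcome (SAP 3.2.4).

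**The concern.** A UTI that came before the injection or the sling cannot be a consequence of either. If it is counted, the reported UTI proportion is too high as a description of what follows treatment. If the early infections are unevenly spread, the between-arm difference moves as well. The SAP's authors know that 8 such events exist, so this is not a hypothetical edge case.

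The two sections also disagree by more than those 8 events. A window opening two weeks after the procedure drops UTIs from day 0 to week 2 as well, and the 9.2 variable keeps them. Two analysts could each follow the SAP faithfully and produce different UTI rows.

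**Working it through.** **1. The plan's own count.** 8 UTIs + 1 fall = 9 pre-treatment events, as stated in SAP 9.2.

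**2. Does any rule remove the 8?**

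| Text | What it restricts | Removes the 8? |
|---|---|---|
| 9.2, UTI and recurrent UTI | Preferred term and recurrent label; time is study duration | No |
| 5.3, safety population | Which women are analysed (treated only) | Only events in untreated women |
| 10.2, treatment-emergent sentence | Events whose onset date is incomplete | No; the SAP already knows these preceded treatment |
| 10.2, UTI row label | Onset after 2 weeks | Yes, but 10.2 defers to 9.2 for definitions |

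By contrast, the catheterization variable in 9.2 is expressly limited to more than 2 weeks after the procedure. The authors wrote a time limit into 9.2 for that outcome and wrote none for UTI.

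**3. How many flags can change?** The variables are per woman and the 8 are events. Dropping a pre-treatment event turns a Yes into a No only if the woman was treated and has no other qualifying record. Each event feeds either the UTI or the recurrent-UTI variable, depending on its label. Over the two variables together, 0 to 8 flags change.

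**4. Size.** Assumption: 73 treated per arm, the planned number randomized (146/2); the treated numbers by arm are not given.

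- Overall rate: at most 8/146 = 5.5 points.
- One arm, if all 8 fall there: at most 8/73 = 11.0 points.
- With 69 per arm instead: 8/138 = 5.8 and 8/69 = 11.6 points.

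**5. Between-arm difference.** Let *b* and *s* be the flags that change in the Botox and sling arms. Counting the events shifts the Botox-minus-sling difference by (*b* − *s*)/73.

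| Split of the 8 (Botox/sling) | Shift if all flags change | Possible range |
|---|---|---|
| 4/4 | 0 | −4/73 to +4/73 = −5.5 to +5.5 |
| 5/3 | 2/73 = 2.7 | −3/73 to +5/73 = −4.1 to +6.8 |
| 6/2 | 4/73 = 5.5 | −2/73 to +6/73 = −2.7 to +8.2 |
| 7/1 | 6/73 = 8.2 | −1/73 to +7/73 = −1.4 to +9.6 |
| 8/0 | 8/73 = 11.0 | 0 to +11.0 |

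Splits towards sling mirror these. The range is wider than the all-change column because women with a later UTI keep their Yes, and those women may lie mostly in one arm.

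**6. How likely is a large shift?** This cannot be estimated from the documents. As an illustration, if the 8 were independent, equally likely in either arm and all flags changed, a split of 5/3 or closer has probability (56 + 70 + 56)/256 = 182/256 = 71%, and 8/0 or 0/8 has 2/256 = 0.8%. If later UTIs occurred at the rates in Protocol Table 3 (an assumption: 24% sling only in ESTEEM, 33% Botox 100 units in ABC), the expected flags changed under a 4/4 split are 4 × 0.67 = 2.68 and 4 × 0.76 = 3.04, a shift of −0.36/73, or about −0.5 points.

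**The case against.** **Counting from randomization may be deliberate.** Both 9.2 and 10.2 say adverse events are reported from randomization, and the pre-treatment events are disclosed openly. It would therefore be wrong to say that 9.2 has no window. It has one, and it differs from the one in 10.2. But an intention-to-treat rationale does not fit: the safety set is confined to treated women, grouped by treatment received, and the table concerns postoperative complications.

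**The sections can be read together.** A programmer could identify UTIs by 9.2 and apply the window in the 10.2 row label, which would exclude the 8. That is a fair reading. A reader might infer that the 8 will certainly be counted, and the documents do not establish that. They leave two defensible derivations.

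**The treatment-emergent sentence in 10.2 implies a distinction.** Defaulting unknown onsets to treatment-emergent makes sense only if other events are not treatment-emergent. However, the SAP never says that known pre-treatment events are dropped, and the sentence refers to a time period that the surrounding text does not define.

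**A tempting stronger reading is that the bias runs against Botox.** Protocol 5.2.2 requires a dip in the week before injection: "If the urine dip is positive the participant will be treated for a urinary tract infection and rescheduled within 4 weeks". A footnote to the SAP 4.6 flow chart leaves the sling dip to usual practice. A reader might infer that most of the 8 lie in the Botox arm. The documents do not support this. Protocol Table 9 and the SAP schedule mark a procedure dip without separating arms, usual practice need not mean seldom done, and nothing says how the 8 were detected or in which arm.

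**The recurrent label is a separate matter.** A woman whose every UTI record is labelled recurrent would be No on the UTI variable. A reader might infer that the UTI row hides infections. No such case is documented, its size is unknown, and the preferred-term summaries in 10.2 are not split by that label. It adds nothing to this point.

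**Conclusion.** The point holds as an inconsistency with a definite direction. SAP 9.2 as written puts 8 known pre-treatment UTIs into the UTI and recurrent-UTI variables for treated women; the 10.2 row would exclude them and also the UTIs of the first two weeks, whose number is not given. Confidence in the mismatch is high.

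The figures of 5.5 points overall and 11.0 points in one arm are ceilings. They need 73 treated per arm, 8 different treated women and no other qualifying UTI record in any of them. The effect on the between-arm difference is unknown in size and sign, and probably small. Safety p-values are descriptive (SAP 7.8 and 10.1), and no efficacy analysis is touched. It is still worth settling because the UTI comparison is a named aim and the remedy is simple.

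**What to change.** 1. In SAP 9.2, require onset on or after the treatment date for both the UTI and the recurrent-UTI variable.
2. List the 9 pre-treatment events separately, so that they stay documented, including the fall that the SAP links to a later serious event.
3. State one UTI window and use it in both 9.2 and 10.2. If the window opening after two weeks is kept, say from which date it runs and show UTIs from treatment to 2 weeks in their own row.

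The cost is a few lines of SAP text and a re-derivation from onset and treatment dates already held; the SAP has already classified the 9 events as pre-treatment. The main table may show slightly fewer UTIs and gain a row. No new data are needed.
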